Imaging of COVID-19 is performed with CXR and CT. Chest radiograph is the initial screening imaging tool in patients with suspicious clinical symptoms of COVID-19 (including fever and lymphopenia). Radiographic appearances are of symmetric patchy or diffuse airspace opacities. Typical CT appearances include peripheral, bilateral ground glass opacity (GGO) which may have a rounded morphology, with or without consolidation. A crazy-paving pattern can be seen with ground glass opacity and intralobular lines. Imaging features depend on when infected patients are imaged. Up to approximately 50% of patients with COVID-19 infection may have normal CT scans 0–2 days after onset of flu-like symptoms [18]. GGO opacity usually develops between day 0 and 4 after symptom onset. The frequency of consolidation increases later in the course of the disease, peaking at 6–13 days with higher rates of bilateral and multilobar involvement. An organising pneumonia pattern is observed with reverse halo or atoll sign and perilobular opacities. About 2–3 weeks after the onset, CT may show varying degrees of clearing of the patchy consolidative opacities, reticular opacities, bronchial wall thickening, and interlobular septal thickening [9]. Imaging (CXR & CT) may be used as an aid in diagnosing COVID-19, guide individual patient management decisions, deal with complications or look for an alternative diagnosis.

With the development of machine learning, deep learning based artificial intelligence (AI) technology has demonstrated tremendous success in the field of medical data analysis due to its capacity of extracting rich features from imaging and complex clinical datasets [10]. Recently, deep learning has been used for diagnosing and distinguishing bacterial and viral pneumonia from thoracic imaging data [11]. In addition, attempts have been made to detect various ECG and chest CT imaging features [12]. In the current COVID-19 pandemic, some preliminary studies have shown promising results for the ECG, chest CT and CXR data analysis and classification [2][3][13]. Besides, small scale initial studies have been done for COVID-19 monitoring [14], screening [15] and prediction of the hospital stay [16].

Exploring the added value of artificial intelligence-assisted disease detection and characterisation may potentially help clinicians to make a prompt correct diagnosis, guide treatment and predict prognosis.

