### 3. STUDY DESIGN

This is a retrospective observational study on patients with suspicious and confirmed COVID-19.

The study aims to recruit up to 2000 patients who will be referred to have ECGs, chest X-rays or CT scans at Chelsea and Westminster Hospital NHS Foundation Trust, Imperial College Healthcare NHS Trust and London North West London University Healthcare NHS Trust, since 1 February 2020.

Patients with suboptimal ECGs, chest radiograph and CT studies due to artefacts will be excluded.

The study will gather data retrospectively and therefore data collection will cease once the prespecified number of participants is reached.

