#### 3.1 STUDY OUTCOME MEASURES

The accuracy with which computer based analysis (machine learning) can diagnose and/or prognosticate Covid-19 infection primarily from ECG, but also from chest xray and CT images.

To determine if computer based analysis (deep learning) enables assessment of the effect of COVID-19 on heart function.

To determine if AI system is superior to cardiology/medical team and/or radiologist assessment.

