### 4. PARTICIPANT ENTRY

#### 4.1 PRE-REGISTRATION EVALUATIONS

Clinical data will be reviewed by a member of the clinical team and the following clinical and laboratory data will be recorded:

- Gender
- Age
- Height/Weight, body mass index
- Medical history (diabetes, hypertension, coronary heart disease, malignancy, structural lung disease, pulmonary heart disease, chronic liver disease, immunosuppressed population)
- The duration of symptoms at the first visit (days, could be inquired from the main complaint of the patient at the first visit, symptoms including fever, dry cough, headache, myalgia, weakness, etc.)

- Smoking status (Never = 0, Ex-smoker = 1, Current = 2, Unknown = 3)
- Pack Years History
- Current NSAID use
- Current ACEi use
- Current Angiotensin receptor blocker use
- Respiratory rate (breaths/min)
- Heart Rate
- Blood Pressure
- Temperature
- Clinical Classification
- oxygen saturation at a rest state (%)
- arterial partial pressure of oxygen (PaO2)/oxygen concentration (FiO2, mmHg)
- Recovery/Death
- Time/date of the CT scanning
- Time/date of the Chest x ray
- D-dimer
- White blood cell count
- Lymphocyte cell count
- platelet count
- C-reactive protein
- Troponin T
- ALT, AST, ALB, ESR, CD3, CD3 count, CD4, CD4 count, CD8, CD8 count, CD19, CD19 count, IL-6, IL-8, IL-10, TNF- $\gamma$
- RT-PCR results for SARS-Cov 2 (Date, results)
- Stay at ICU (days)
- Hospital Stay (days)
- Date of death
- Cause of death
- Intubation
- Date of Intubation
- Time mechanical Ventilation (days)
- NEWS score on arrival

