#### 4.2 INCLUSION CRITERIA

To be included in this study the patient must:

- have ECGs, Chest x-ray and/or chest CT imaging (with or without contrast)
- positive laboratory Covid-19 virus nucleic acid test (RTPCR assay with throat swab samples) or clinical suspicion for Covid-19 infection
- be aged >18 years

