## **6. STATISTICS AND DATA ANALYSIS**

Machine learning algorithms will be trained to differentiate between patient groups (e.g. based on diagnosis or prognosis). For example, for the ECG analyses, in addition to conventional morphological features of QRS, we propose to analyse both temporal and spectrum features of the 12-lead ECG. The spectrum features would include band-powers of different frequency bands, and coefficients of auto-regression (AR) models of different orders would be used as temporal features. Moreover, the temporal stability of features (i.e., how the features vary from beat to beat) and the spatial dispersion of these features (i.e., who the features vary across the 12 leads) will also be investigated.

Data will be analysed by the chief investigator and the research team at the National Heart and Lung Institute, Imperial College London. Anonymised data may be shared with collaborators, for example at University College London, for data processing subject to any required data sharing agreements/approval being in place before the data is transferred.

Data and all appropriate documentation will be stored for a minimum of 10 years after the completion of the study, including the follow-up period.

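### No final diagnosis is recorded for any patient, so an ECG model's diagnostic accuracy could not be attributed to COVID-19 rather than to unequal shares of acute cardiac disease.

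*Combined protocol and SAP*

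**What the plan says.** The Study Summary gives diagnosis, mainly from the ECG, as the aim. The first outcome in section 3.1 is "The accuracy with which computer based analysis (machine learning) can diagnose and/or prognosticate Covid-19 infection primarily from ECG", with chest X-ray and CT as further sources.

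Section 3 describes the population: "This is a retrospective observational study on patients with suspicious and confirmed COVID-19". Section 4.2 admits patients with a positive RT-PCR test "or clinical suspicion for Covid-19 infection". There is no separate control group. The eligibility text in the Study Summary omits the word positive, so on that wording patients who tested negative could also enter. The point below is the same on either wording.

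Section 4.1 lists the data to be recorded. The diagnostic label is "RT-PCR results for SARS-Cov 2 (Date, results". The nearest other items are past medical history (including coronary and pulmonary heart disease), troponin T, D-dimer, recovery or death, cause of death, and a clinical classification that is not defined. No final, discharge or alternative diagnosis is listed.

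The exclusions in 4.3 concern artefacts and the interval to the RT-PCR test. They do not remove patients with another acute illness. Section 6 says "Machine learning algorithms will be trained to differentiate between patient groups (e.g. based on diagnosis or prognosis". It does not say who counts as a case or a non-case, and it plans no breakdown of accuracy by what the non-cases had.

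**The concern.** Diagnostic accuracy needs non-cases, and under 4.2 these can come only from patients who were ill enough to be suspected but were not confirmed. Some may have had heart failure, acute coronary disease or pulmonary embolism, all of which can change the ECG. If such illness is commoner in non-cases, a model can learn that a cardiac ECG points away from COVID-19. If it is commoner in cases, the model can learn the reverse. Either way it could discriminate without using any ECG change specific to COVID-19.

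Two statements in section 1.2 would be affected. The first is that specific ECG effects of COVID-19 are not yet known: a positive diagnostic result would be read as evidence of them. The second is the hypothesis that the algorithms will work in other patients: accuracy that rests on the local mix of competing illnesses may not carry over to another mix.

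**Working it through.** The plan gives no figure to reproduce. The target of up to 2000 patients comes without a precision target, a case split or an accuracy metric. The check is therefore a reading of sections 3.1, 4.1, 4.2, 4.3 and 6, followed by an illustration.

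**Inputs, all assumed, because the documents give none of them**
- h: share of non-cases with acute cardiac disease, 20% to 40%.
- c: share of cases with acute cardiac disease, 0% to 20%.
- Model flags a cardiac ECG in 70% of patients with acute cardiac disease and in 15% of others.
- Rule: no cardiac flag, so call COVID-19. It contains no COVID-19-specific information.

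**Formulas**
- Specificity = 0.70h + 0.15(1 - h).
- Sensitivity = 1 - [0.70c + 0.15(1 - c)].
- AUC of one binary rule = (sensitivity + specificity)/2 = 0.5 + 0.275(h - c).

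**Results**
- Specificity: 0.14 + 0.12 = 0.26 at h = 20%; 0.28 + 0.09 = 0.37 at h = 40%.

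| c | Sensitivity | AUC, h = 20% | AUC, h = 40% |
|---|---|---|---|
| 0% | 0.85 | 0.555 | 0.61 |
| 15% | 0.7675 | 0.514 | 0.569 |
| 20% | 0.74 | 0.50 | 0.555 |

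The AUC is 0.50 whenever h = c. If c exceeds h, the reversed rule gains 0.275(c - h).

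**Could a small effect look real?** Assume 1000 cases and 1000 non-cases, with sensitivity 0.85 and specificity 0.26. The standard error of the AUC is 0.5 x sqrt(0.85 x 0.15/1000 + 0.26 x 0.74/1000) = 0.0089. The 95% interval is 0.555 ± 0.0175, or about 0.54 to 0.57, which excludes chance.

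**What a recorded diagnosis would show**
- Specificity by group: 0.70 in acute cardiac non-cases and 0.15 in the rest.
- Acute cardiac disease removed from both groups: sensitivity 0.85, specificity 0.15, AUC 0.50. The apparent signal disappears.
- Removed from non-cases only, with c = 20%: the rule that a cardiac ECG means COVID-19 has sensitivity 0.14 + 0.12 = 0.26, specificity 0.85 and AUC 0.555. One-sided removal creates the same kind of artefact in the other direction.

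**The case against.** **The accuracy is not false.** A reader might infer that the true AUC is 0.50 and that any excess is an error. The documents do not support that. Among patients who are RT-PCR positive or suspected, recognising another cause of illness is useful diagnostic information, and 0.555-0.61 would be the rule's real accuracy there. This objection stands. Only attribution and transfer remain in question.

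**The effect may be small or absent.** A reader might also infer that a model trained under this plan will in fact work by recognising other heart disease. Nothing in the documents gives h or c. Section 1.1 names myocarditis among the manifestations of COVID-19, and sections 2 and 3.1 set out to study cardiac effects, so c = 0 cannot be taken for granted. This stands too, and the range must include no effect.

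**Existing fields help.** Troponin T, D-dimer, past history and cause of death allow some checking. This stands in part. Troponin T may also be raised by cardiac involvement in cases, history is not the index illness, and cause of death covers only those who died. If clinical classification means final diagnosis, the gap closes, but its place among the presentation observations does not suggest this.

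**Non-cases are not defined.** Section 1.2 would develop algorithms from confirmed or suspected patients together, and section 1.1 puts RT-PCR sensitivity at 60-95%. It is therefore too strong to infer that every unconfirmed patient had something else. With an assumed 50% prevalence among suspected patients and perfect RT-PCR specificity, the infected share of negatives is 0.20/0.70 = 29% at 60% sensitivity and 0.025/0.525 = 5% at 95%. This is a linked gap and belongs in the repair.

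**Conclusion.** The omission is confirmed: 4.1 records no final or discharge diagnosis, and no other section supplies one. If acute cardiac disease differs in frequency between cases and non-cases, an ECG model could separate the groups on that difference. The plan could then only partly check whether the result reflects COVID-19.

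The size is unknown. Under the assumed detection rates, the AUC gain runs from nil when the shares are equal to 0.11 when 40% of non-cases and no cases are affected. The conclusion assumes that unconfirmed suspected patients serve as non-cases, which is the only reading under which the diagnostic outcome can be estimated.

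The point limits how the diagnostic result can be interpreted. It does not touch the primary objective in section 2, which concerns course and severity in patients with COVID-19. It is a worthwhile, inexpensive improvement and not a flaw that invalidates the study.

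**What to change.** - **Section 4.1:** add the primary discharge diagnosis for every patient, cases and non-cases. Also note any acute cardiac diagnosis in the same admission, because a case may have COVID-19 as the primary diagnosis. Do this before extraction and anonymisation; going back to the records may be difficult afterwards. If clinical classification is meant to be this item, define it.
- **Section 6, groups:** state which patients count as cases and non-cases, including how RT-PCR-negative and untested suspected patients are handled.
- **Section 6, reporting:** give specificity by non-case group: other respiratory infection, acute cardiac, other.
- **Section 6, repeat analysis:** rerun the ECG diagnostic analysis with acute cardiac diagnoses removed from both groups, or stratified by them. Describe a result as a COVID-19 ECG signal only if discrimination persists there.

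**Cost:** a little more to extract in a review of existing records, and one repeat analysis. The restricted analysis has a smaller sample and sets aside cases with COVID-19 cardiac involvement, so it should be reported beside the full analysis and not replace it.

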#### 4.3 EXCLUSION CRITERIA

The presence of any of the following will preclude the patient from the study:

1. Suboptimal ECGs, chest radiographs or CT studies for deep learning methods due to artefacts including severe motion artefacts which causes blurring of the contours of or significant artefacts due to metallic prosthesis which causes image degradation
2. Time-interval between ECGs, chest CT and the RT-PCR assay was longer than 7 days

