### 1.2 RATIONALE FOR CURRENT STUDY

Coronavirus Disease 2019 (COVID-19) has been widespread worldwide since December 2019. It is highly contagious, and severe cases can lead to acute respiratory distress or multiple organ failure and ultimately death. The disease can be confirmed by using the reverse-transcription polymerase chain reaction (RT-PCR) test. ECGs, Chest x-rays and CT scans are rich sources of data that provide insight to disease that otherwise would not be available. Knowing who to admit to the hospital or intensive care saves lives as it helps to mitigate resource shortages. Novel Artificial Intelligence tools such as Deep learning will allow a complex assessment of the Imaging and clinical data that could potentially help clinicians to make a faster and more accurate diagnosis, better triage patients and assess treatment response and ultimately better prediction of outcome.

Our group has significant experience implementing machine learning algorithms on vast quantities of ECGs, such as from the UK Biobank, and propose to extend our techniques to data from patients with Covid-19.

ECGs are routinely performed on unwell patients presented to hospital and often have serial recordings during their inpatient stay. This provides a unique method by which disease progression can be tracked using a simple, non-invasive and inexpensive method throughout the course of the illness. Furthermore, whether COVID-19 causes specific ECG changes is not known. Identifying and understanding ECG changes related to COVID-19, particularly those features that may predict clinical outcomes, would be especially useful. The non-invasive, quick and easy nature of recording ECGs in unwell patients makes it an ideal modality to investigate and predict COVID-19 related outcomes.

As the manifestation of COVID-19 and related complications on ECG is currently unknown, we hypothesise that beyond routine radiographic imaging, ECG can provide an insight into clinical outcomes related to COVID-19 that can be helpful for prognostication.

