## 2. STUDY OBJECTIVES

### Primary objectives

- We will investigate if the standard electrocardiogram (ECG), which is a conventional clinical tool used record the electrical activity of the heart, a chest X-ray and/or a CT scan, can be used to predict the course and severity of disease in patients with Coronavirus Disease 2019 (COVID-19).

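### The artefact exclusion works on the whole patient, so a poor radiograph or CT can remove a usable ECG from an ECG-led analysis

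*Combined protocol and SAP*

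**What the plan says.** Section 4.3 (Exclusion criteria) opens with "The presence of any of the following will preclude the patient from the study". Its first item is "Suboptimal ECGs, chest radiographs or CT studies for deep learning methods due to artefacts including severe motion artefacts", followed by two qualifications: blurring of contours, and metallic-prosthesis artefact that degrades the image. The unit is therefore the patient, and the modalities are joined by *or*.

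Section 3 (Study design) repeats the exclusion, also at patient level, but joins the modalities with *and* and does not mention deep learning: "Patients with suboptimal ECGs, chest radiograph and CT studies due to artefacts will be excluded".

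Three other statements bear on the consequence:

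- Section 4.2 admits patients on one or more modalities: "have ECGs, Chest x-ray and/or chest CT imaging (with or without contrast").
- Section 3.1 defines the first outcome as accuracy "primarily from ECG, but also from chest xray and CT images".
- Section 3 says that "data collection will cease once the prespecified number of participants is reached", with a ceiling of 2000 patients.

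Section 6 (Statistics and data analysis) does not say that unusable recordings will be counted or reported. No section limits the exclusion to the affected recording or modality.

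**The concern.** The entry rule and the main outcome treat the modalities separately, while the exclusion rule ties them together. A patient with a sound ECG and a blurred CT is eligible under section 4.2 and informative for the main outcome in section 3.1, yet is removed by section 4.3. The faults that section 4.3 describes are mostly imaging faults that need not touch the ECG.

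Selection is at stake more than numbers. Collection continues to a target, so excluded patients can be replaced while the pool lasts. The primary objective in section 2 is to predict course and severity, and section 1.2 promotes the ECG for sick patients: "The non-invasive, quick and easy nature of recording ECGs in unwell patients makes it an ideal modality". If artefact is related to severity, a patient-level rule alters the severity mix of the ECG analysis through faults in other tests. With no tally planned, a reader could not see whether this had happened.

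**Working it through.** The plan gives no figure to reproduce: no artefact rate, target accuracy, or share of patients with all three modalities. **Every rate below is an assumption.**

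**Step 1. What the text implies.** Take a patient with a usable ECG and a CT spoiled by artefact.

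- Section 4.2: eligible.
- Section 4.3 (*or*, patient level): excluded.
- Section 3 with *and* read as a list: excluded.
- Section 3 with *and* read as all three poor: kept.

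Only the last reading keeps the patient, and section 4.3 does not say that.

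**Step 2. How many patients.** Let p be the artefact rate in each modality, with all three present. If faults are independent:

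- excluded under *or* = 1 − (1 − p)³
- excluded with a usable ECG = (1 − p) × [1 − (1 − p)²]

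Without independence, the first lies between p (faults always coincide) and 3p (faults never coincide), and the second between 0 and 2p.

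| p | Excluded, independent | Bounds | Excluded with usable ECG, independent | Bounds |
|---|---|---|---|---|
| 5% | 1 − 0.95³ = 14.3% | 5–15% | 0.95 × 0.0975 = 9.3% | 0–10% |
| 10% | 1 − 0.90³ = 27.1% | 10–30% | 0.90 × 0.19 = 17.1% | 0–20% |

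At 5%, 9.3/14.3 = 65% of those excluded had a usable ECG.

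With an ECG and one other modality, the share excluded with a usable ECG is p(1 − p) = 4.75% at p = 5% (bounds 0–5%). With an ECG only, it is 0.

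**Step 3. Severity mix.** Assume 30% severe at screening, and artefact rates per modality of 10% in severe and 5% in other patients. If r_s and r_o are the proportions retained, the severe share after exclusion is 0.30 r_s / (0.30 r_s + 0.70 r_o).

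Under recording-level exclusion, r_s = 0.90 and r_o = 0.95 for the ECG analysis: 0.27/0.935 = 28.9%.

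Under the patient-level *or* rule, r_s lies between 0.70 (no overlap of faults) and 0.90 (complete overlap), and r_o between 0.85 and 0.95:

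| Overlap in severe | Overlap in others | Severe share |
|---|---|---|
| none (0.70) | complete (0.95) | 0.21/0.875 = 24.0% |
| none (0.70) | none (0.85) | 0.21/0.805 = 26.1% |
| independent (0.90³) | independent (0.95³) | 0.2187/0.8189 = 26.7% |
| complete (0.90) | complete (0.95) | 0.27/0.935 = 28.9% |
| complete (0.90) | none (0.85) | 0.27/0.865 = 31.2% |

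The range is 24.0–31.2%, on both sides of 28.9%. Even if sicker patients have more artefact, the extra shift from the patient-level rule could go either way.

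**The case against.** **Sections 3 and 4.3 contradict each other.** A reader might infer this from *and* against *or*. The text does not establish it. The section 3 sentence is most naturally an ordinary list with the same meaning as section 4.3. It is an ambiguity to reconcile. On the list reading, both sections remove usable ECGs, so the concern survives.

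**One poor tracing excludes the patient.** Section 1.2 expects serial ECGs, and the plural in section 4.3 may mean the patient's ECGs as a set. The documents do not settle this.

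**Usability is tailored to the method under test, which flatters the algorithm or favours it over doctors.** Section 4.3 does judge recordings by the needs of deep learning. But its examples are ordinary image-quality faults, qualified as severe or significant, that could hamper human readers too. Nothing in the documents shows a direction for the comparison with clinicians, and none is claimed here.

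**The rule strips out the sickest patients.** No section says that artefact is commoner in severe disease, and step 3 shows no fixed direction even if it is.

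**The figures take a favourable case.** This stands. Three modalities per patient is not required by section 3 or 4.2, and the effect shrinks to zero as patients have fewer tests.

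**Quality exclusions are normal.** They are, and this point does not oppose them. It concerns the unit to which they apply and whether they are counted.

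**Conclusion.** The point holds in a limited form. As written, section 4.3 removes patients with a usable ECG for faults in another modality, and no other section clearly undoes this. That conclusion rests on the text alone.

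Its size cannot be derived from the documents. The illustrative loss of about 9% of patients with a usable ECG depends on a 5% rate, independence and three modalities for everyone. The severe share of 24.0–31.2% depends on the assumed 10%, 5% and 30%. The direction of any effect on accuracy is unknown. The change is worth making because it keeps usable data for the main outcome at little cost, not because a large bias has been shown.

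**What to change.** Replace the artefact sentence in section 3 and item 1 of section 4.3 with one rule: *A recording unusable because of artefact is excluded; the patient stays in for every modality with at least one usable recording.* Because the opening line of section 4.3 acts on the patient, the rule should stand outside that list.

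Add two short provisions:

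- Usability is judged by a written rule, without knowledge of RT-PCR result or outcome. This is a precaution: the data are retrospective, so both may already be known when recordings are screened.
- The number and share of unusable recordings are reported by modality and by severity, using data already listed in section 4.1 (NEWS on arrival, intubation, ICU stay, death).

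The main ECG analysis would still rest on usable ECGs only; the tally lets a reader judge how far that matters. A sensitivity analysis counting unusable recordings as incorrect is optional. For an assumed accuracy of 0.85 and 5% unusable, it gives 0.95 × 0.85 = 0.81. That drop follows from the scoring rule and does not measure bias.

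The cost is wording in two sections and a small tally. The downside is that modality results would rest on partly different patients, so comparisons between modalities need a common subset.

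### The 7-day limit to RT-PCR covers ECG and chest CT but omits the chest X-ray, so films at any interval from the swab can enter the diagnostic analysis

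*Combined protocol and SAP*

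**What the plan says.** Section 4.2 lets a patient in on any one of three modalities: "have ECGs, Chest x-ray and/or chest CT imaging (with or without contrast". The disease criterion in the same section is "positive laboratory Covid-19 virus nucleic acid test (RTPCR assay with throat swab samples) or clinical suspicion for Covid-19 infection". Section 3.1 defines the outcome as the accuracy of machine diagnosis or prognosis "primarily from ECG, but also from chest xray and CT images".

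Section 4.3 has two exclusions. The first concerns quality and names every modality: "Suboptimal ECGs, chest radiographs or CT studies for deep learning methods due to artefacts". The second concerns timing and names two: "Time-interval between ECGs, chest CT and the RT-PCR assay was longer than 7 days". Under the opening line of section 4.3, meeting either exclusion removes the patient, not just the recording.

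Section 4.1 lists both dates that an X-ray rule would need: "Time/date of the Chest x ray" and "RT-PCR results for SARS-Cov 2 (Date, results".

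**The concern.** The timing exclusion is the only rule that ties a recording to the test that defines disease status, and it passes over one of the three modalities under study. Section 1.2 gives that modality a leading place in practice: "Chest radiograph is the initial screening imaging tool in patients with suspicious clinical symptoms of COVID-19". The same section says that what imaging shows varies with when the patient is imaged, and describes CT findings that develop, peak and then partly clear.

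If a radiograph and a swab belong to different stages of illness, the PCR result is a weaker reference for that film. At stake is the chest X-ray part of the diagnostic accuracy outcome, in training and in testing. Two further aims could be touched where they rely on radiographs: the comparison with radiologists in section 3.1, and any reading of X-ray accuracy beside that of CT or ECG.

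**Working it through.** The plan gives no derived figure to reproduce: the 2000 patients are a cap without a calculation. The check is mainly a comparison of sections.

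**1. Which modalities does each rule cover?**

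| Provision | ECG | Chest X-ray | Chest CT |
|---|---|---|---|
| Entry, section 4.2 | yes | yes | yes |
| Accuracy outcome, section 3.1 | yes (lead) | yes | yes |
| Artefact exclusion, section 4.3 item 1 | yes | yes | yes |
| 7-day exclusion, section 4.3 item 2 | yes | **no** | yes |
| Recording date listed in section 4.1 | no | yes | yes |

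The chest X-ray is the only modality without an interval limit. For a patient who enters on X-ray alone, item 2 has nothing to act on. For a patient who also has an ECG or CT, it checks those recordings and leaves the film unchecked.

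**2. Does another section close the gap?** The only other time bound is a calendar start, given as 1 February 2020 in section 3 and 15 May 2020 in the study summary. Neither is linked to symptoms, admission or swab. Section 6 says that algorithms will separate patient groups by diagnosis or prognosis, but gives no rule for choosing a film or attaching a label to it. The X-ray and RT-PCR dates are recorded, but no rule compares them.

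**3. What does the wording allow?** Two invented examples, in days from symptom onset:

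- Swab on day 1, image on day 9: the gap is 9 − 1 = 8 days. A CT excludes the patient; a radiograph does not.
- Swab on day 3, radiograph on day 21: the gap is 21 − 3 = 18 days. The film is kept.

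**4. Which way would accuracy move?** Section 1.2 gives a time course for CT: up to about 50% normal at days 0–2, consolidation most frequent at days 6–13, varying degrees of clearing at about 2–3 weeks. If radiographs followed a similar course, which is an inference, the day-9 film would fall near peak abnormality and the day-21 film in the clearing phase. Both are kept, and they pull in opposite directions.

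Let p be the share of films from PCR-positive patients that lie outside the window, S_in the sensitivity inside it and S_out the sensitivity outside it. Then

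measured sensitivity = (1 − p) × S_in + p × S_out,

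and the shift from S_in is p × (S_out − S_in). The documents give none of these three values. With assumed S_in = 0.85 and p from 0.05 to 0.20, and S_out at its two extremes:

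| p | S_out = 0 | S_out = 1 |
|---|---|---|
| 0.05 | 0.95 × 0.85 = 0.81 | 0.81 + 0.05 = 0.86 |
| 0.20 | 0.80 × 0.85 = 0.68 | 0.68 + 0.20 = 0.88 |

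Under these assumptions measured sensitivity could lie anywhere from 0.68 to 0.88 around a true in-window value of 0.85. The table shows that the sign is open; it is not an estimate.

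**The case against.** The strongest reply is that the omission is probably a drafting slip with little effect. Section 1.2 places the radiograph at first assessment of symptomatic patients, so most films should lie close to the swab. ECG is the lead modality and is covered by the limit. The stated primary objective is to predict course and severity, where the interval to the swab matters less than it does for diagnosis. All of this stands, and it limits the likely effect. It does not remove the gap, because whoever extracts the data will apply the criterion as worded.

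A reader might also infer more than the text supports:

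- **That X-ray accuracy will be understated.** This requires out-of-window films to read as normal. The clearing in section 1.2 is described for CT, is of varying degree, and appears alongside other persisting abnormalities. Films near the peak could raise sensitivity.
- **That mistimed films will in fact carry a COVID-19 label.** The documents do not say how labels attach to individual images. The text permits this; it does not state it.
- **That a planned comparison between modalities is spoiled.** Sections 2 and 3.1 plan none. Unequal timing matters only if readers set the three accuracies side by side.
- **That the comparison with doctors is biased towards one side.** If both read the same films, which the protocol does not specify, label error affects both.

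**Conclusion.** The point holds as a gap in the eligibility rule. The 7-day limit omits the chest X-ray, nothing elsewhere supplies one, and the protocol's own account of imaging over time gives reason to want it. The consequence is possible distortion of chest X-ray diagnostic accuracy, of unknown direction and size. Confidence is high on the omission and low on any particular bias.

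The consequence rests on one assumption: that films will be judged against the patient's PCR status, as the patient-level criterion in section 4.2 suggests. It affects the diagnostic use of one modality out of three, and should be corrected before data extraction and model training.

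**What to change.** Extend the existing 7-day limit to the radiograph used in the diagnostic analysis, at image level. For example: *for the diagnostic analysis, a chest radiograph taken more than 7 days before or after the RT-PCR assay is not used; the patient's other eligible recordings are retained.* State also which film is used when a patient has several. If X-rays were left without a limit on purpose, give the reason.

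The level matters. Simply adding the radiograph to item 2 would let one late film remove the whole patient, including valid ECG or CT data, because section 4.3 excludes patients and not images.

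The change takes a sentence or two and uses dates already on the section 4.1 list. Its cost is the loss of some radiographs from the diagnostic set; the documents do not allow that number to be estimated.

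Two related gaps remain. Patients entered on clinical suspicion without an RT-PCR have no anchor date for any modality, and this change does not resolve that. Section 4.1 also lists no ECG date, which the existing limit needs.
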